### **8.9 Injection Site Pain**

Descriptive statistics for VAS scores for pain perception will be tabulated by treatment formulation and disease type at each injection (predose and after dose). Investigator's assessment of most recent injection site including pain, swelling, redness, and induration will be reported in 4-point categorical scale (absent, mild, moderate and severe) and will be summarized by treatment formulation and disease type at each injection (predose and after dose).

### **8.10 Special Interest Adverse Events**

Incidence of treatment emergent special interest adverse events will be tabulated by treatment formulation and MedDRA preferred terms for EPS-related AEs, weight-related AEs, glucose-related AEs, lipid-related AEs, white blood cell abnormalities, orthostasis-related AEs, prolactin-related AEs, QT-interval AEs, suicidality -related AEs and injection-site-related AEs. In addition, proportion of subjects received anticholinergic medication for treatment-emergent EPS-related events will be presented.

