#### 1.4 Risks and Benefits

Abilify Maintena is marketed worldwide and is approved for schizophrenia and bipolar I disorder. To date, no unexpected safety concerns have been reported. The most frequently observed adverse reactions for approved indications are weight increased and akathisia.

Based on a 12-week, double-blind, placebo-controlled trial of Abilify Maintena in adult subjects with schizophrenia, the most commonly observed adverse reactions associated with the use of Abilify Maintena (incidence of 5% or greater and aripiprazole incidence at least twice that for placebo) were increased weight (16.8% versus 7.0%), akathisia (11.4% versus 3.5%), injection site pain (5.4% versus 0.6%), and sedation (5.4% versus 1.2%).

Based on a double-blind, placebo-controlled, randomized withdrawal (maintenance) trial, the most commonly observed adverse drug reactions that were associated with the use of

Protocol 031-201-00181

Abilify Maintena (incidence of 5% or greater and aripiprazole incidence greater than placebo) were weight increased (22.7%) and akathisia (20.5%).

Other commonly reported adverse reactions (reported in 2% or more of Abilify Maintena-treated subjects and at a greater proportion than in the placebo group) during the trials included the following:

- Eye disorders: vision blurred
- Gastrointestinal disorders: constipation, dry mouth, diarrhea, vomiting, and abdominal discomfort
- Infections and infestations: upper respiratory tract infection
- Investigations: decreased weight, blood creatine phosphokinase increased
- Metabolism and nutrition disorders: increased appetite
- Musculoskeletal and connective tissue disorders: arthralgia, back pain, myalgia, and musculoskeletal pain
- Nervous system disorders: dizziness somnolence, sedation, bradykinesis, and tremor
- Psychiatric disorder: anxiety and depression
- Respiratory, thoracic, and mediastinal: nasal congestion
- Reproductive system and breast disorders: erectile dysfunction

In addition to the above, the list of adverse reactions associated with the use of Abilify Maintena or other antipsychotic/atypical antipsychotic drugs includes the following:

- Neuroleptic malignant syndrome
- Tardive dyskinesia
- Metabolic changes that include hyperglycemia/diabetes mellitus, dyslipidemia, and weight gain
- Orthostatic hypotension
- Falls
- Sleep apnea
- Leukopenia, neutropenia, and agranulocytosis
- Impairment of judgment, thinking, or motor skills

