## 4.2 Restricted Medications

Benzodiazepine use is allowed up to a maximum of 6 mg/day lorazepam or equivalent, but not within 8 hours of any rating scales during the trial. The use of IM lorazepam is also permitted for emergent agitation, but only if deemed absolutely necessary by the investigator. The following guide should be used to determine approximate lorazepam equivalents: 1 mg lorazepam = 5 mg diazepam = 15 mg oxazepam = 15 mg clorazepate. Subjects must not be on more than one benzodiazepine beyond the screening visit.

If a subject is receiving 2 benzodiazepines at the screening visit (eg, lorazepam and oxazepam), attempts should be made to discontinue one of the benzodiazepines, if clinically warranted, to allow potential subjects to enter the trial. The second benzodiazepine should be tapered off over an appropriate amount of time within the

Protocol 031-201-00181

30-day screening period to prevent side effects, and the subject should be maintained on the remaining benzodiazepine for at least 14 days prior to the administration of IMP.

Benzodiazepine and non-benzodiazepine use is allowed during the trial as needed to manage AEs such as agitation, anxiety, sleep disturbance, and insomnia. Combined use of both drug classes (ie, benzodiazepines and non-benzodiazepine sleep aids) as treatment for insomnia is not allowed. Benzodiazepine use should be discontinued as soon as the AE for which it was initiated subsides, as per the investigator's discretion, to avoid any withdrawal effects.

Medications that are restricted during the trial are listed in [Table 4.2-1](#).

| Table 4.2-1 Medications Restricted During the Trial |                                      |   |
|--|--------------------------------------|---|
| Medication  | Screening                     | Treatment Period   |
| Anticholinergics a                              | ≤ 4 mg/day benztropine or equivalent | ≤ 4 mg/day benztropine or equivalent  |
| Propranolol (for akathisia or tremor) b, c      | Maximum 60 mg propranolol per day    | Maximum 60 mg propranolol per day   |
| Benzodiazepines b                               | -                                    | No more than one benzodiazepine and not in combination with other sleep aid medication |

aAnticholinergics are not allowed within 12 hours of any rating scales during any phase of the trial.

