bPropranolol is not allowed within 8 hours of any rating scales during any phase of the trial.

cSubjects receiving propranolol for heart disease may remain on stable, pretrial doses, as needed, throughout the trial, so long as the total dose does not exceed 60 mg/day.

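### SAP 8.10 summarises drug treatment of EPS events by anticholinergic use alone, so akathisia or tremor treated with propranolol and no anticholinergic is not counted in that proportion

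*SAP*

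**What the plan says.** SAP 8.10 first plans the EPS adverse event table: "Incidence of treatment emergent special interest adverse events will be tabulated by treatment formulation and MedDRA preferred terms for EPS-related AEs", alongside other event groups. It then adds one summary of drug treatment for these events: "proportion of subjects received anticholinergic medication for treatment-emergent EPS-related events will be presented". No other section of the readable SAP ties a medication to an EPS event.

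Protocol 4.2 restricts, but permits, two drug groups that bear on EPS. Table 4.2-1 allows anticholinergics at "≤ 4 mg/day benztropine or equivalent", with no symptom named. It lists the other as "Propranolol (for akathisia or tremor"), with a daily maximum. A footnote recognises a second reason for taking it: "Subjects receiving propranolol for heart disease may remain on stable, pretrial doses".

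Protocol 1.4 indicates how common the relevant event may be: "The most frequently observed adverse reactions for approved indications are weight increased and akathisia". In the 12-week placebo-controlled trial of the 400 mg depot the figure is "akathisia (11.4% versus 3.5"%). In the randomised-withdrawal trial the depot figures are "weight increased (22.7%) and akathisia (20.5"%).

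**The concern.** Safety and tolerability is a primary objective (Protocol 2.3.1, SAP 2.1), and the EPS scales are among the primary safety variables. The proportion of subjects who needed a drug for an EPS event is a natural companion to the incidence table, because it shows how often an event led to drug treatment.

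As SAP 8.10 stands, the count depends on which permitted drug was given. Two subjects with the same akathisia event, one given an anticholinergic and one given propranolol, fall on opposite sides of it. Akathisia is the leading EPS-type reaction in the protocol's own figures, and Protocol 1.4 also lists tremor among the commonly reported reactions. The omitted drug is thus the one that the protocol labels for these two symptoms. What is at stake is the completeness of one descriptive figure in the safety report.

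**Working it through.** The plan states no figure for this proportion, so there is nothing to reproduce. The check is a comparison of texts, followed by an illustration of size.

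**Who is counted in the SAP 8.10 proportion**

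| Treatment of a treatment-emergent akathisia or tremor event | Counted? |
|---|---|
| Anticholinergic only | Yes |
| Anticholinergic and propranolol | Yes |
| Propranolol only | No |
| Other medication only | No |

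**Whether another table recovers the third row**

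- SAP 7.4 tabulates concomitant medication by drug class and time period in the randomized sample. Propranolol falls within its scope, but the table has no link to an EPS event and would mix in use for heart disease. Benzodiazepines get their own summary there; propranolol does not.
- SAP 8.2 (adverse events by preferred term and severity), SAP 8.10 (EPS-related events) and SAP 8.8 (BARS, SAS and AIMS) report the events and scores but not whether a drug was given.
- Protocol 3.7.4 requires medications taken to treat an adverse event to be recorded on the eCRF, so the information needed is collected.

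**Illustration of size**

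Inputs: n = 129 per arm (Protocol 3.3, SAP 3); akathisia rate p = 0.114 or 0.205 (Protocol 1.4); share s of akathisia cases treated with propranolol and no anticholinergic. The documents do not give s; 10%, 25% and 50% are assumptions.

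Cases per arm = n × p: 129 × 0.114 = 14.7; 129 × 0.205 = 26.4.

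Subjects missed per arm = n × p × s:

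| s (assumed) | p = 0.114 | p = 0.205 | Shortfall in the proportion, p × s |
|---|---|---|---|
| 10% | 1.5 | 2.6 | about 1 to 2 percentage points |
| 25% | 3.7 | 6.6 | about 3 to 5 percentage points |
| 50% | 7.4 | 13.2 | about 6 to 10 percentage points |

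Protocol 7.1 gives total enrolment as 152 to 258. At the lower end there are 152 / 2 = 76 per arm, hence 76 × 0.114 = 8.7 to 76 × 0.205 = 15.6 cases. The number missed is then about 0.9 to 1.6 at s = 10% and 4.3 to 7.8 at s = 50%. The shortfall in percentage points does not change with n.

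**The case against.** The strongest case against acting is that the statistic is accurately labelled. SAP 8.10 says that it presents anticholinergic use and does not claim to measure all drug treatment of EPS. Protocol 7.6 asks for no summary of EPS medication, so the SAP already goes further than required and the two documents do not conflict. This is right as far as it goes: the point is an incomplete summary, not an error or a contradiction.

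A reader might infer more, in three ways that the documents do not support.

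- *That treated akathisia drops out of the safety report, so both formulations look better tolerated on EPS than they are.* Every treatment-emergent akathisia event, treated or not, is counted by preferred term under SAP 8.10 and by severity under SAP 8.2, and akathisia is scored on the BARS under SAP 8.8. Only one supplementary proportion is affected, and the same counting rule applies to both randomised arms.
- *That the protocol assigns propranolol, and not anticholinergics, to akathisia.* Table 4.2-1 sets limits on permitted drugs. It places no symptom limit on anticholinergics, and akathisia treated with one is counted.
- *That untabulated propranolol use distorts the mean BARS and SAS changes.* The documents give no estimate of such an effect. Protocol 4.2 also bars propranolol within 8 hours, and anticholinergics within 12 hours, of any rating scale. These intervals may not remove all influence. Knowing the proportion treated would help in reading the scores, but bias in them is not shown.

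Two further cautions stand. The akathisia rates come from other trials of the 400 mg depot, whereas this trial enrols clinically stable subjects with established tolerability to aripiprazole and has a 960 mg arm. Pages after SAP Appendix 3 are redacted, so whether a further table covers this use cannot be checked.

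**Conclusion.** The point holds in a narrow form and is minor. Read as the need for EPS medication, the SAP 8.10 proportion is too low by the number of subjects whose treatment-emergent akathisia or tremor was treated with propranolol and no anticholinergic. No sample size, error rate or hypothesis test depends on it.

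The size cannot be fixed from the documents. The illustrative range of about 1.5 to 13 subjects per arm rests on full enrolment of 129 per arm, on akathisia rates carried over from earlier trials to both arms, and on an assumed share of 10% to 50%. It does not include tremor. If propranolol alone is rarely used, the shortfall is negligible.

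**What to change.** In SAP 8.10, replace the anticholinergic-only proportion with this: the proportion of subjects who received any medication recorded on the eCRF as given for a treatment-emergent EPS-related event, by treatment formulation, overall and split into anticholinergic, propranolol and other. State that propranolol taken for heart disease is excluded. The anticholinergic line keeps the figure now planned, so nothing is lost.

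The cost is one sentence in the SAP and two or three extra rows in one table. No new data are needed, because Protocol 3.7.4 already requires medications given for an adverse event to be recorded. The change concerns reporting only and makes no recommendation on which drug or dose to use.

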## **9 Efficacy Analyses**

Efficacy assessments for all subjects includes Clinical Global Impression - Improvement (CGI-I) and Subjective Well-being under Neuroleptic Treatment - Short Form (SWN-S). The Positive and Negative Syndrome Scale (PANSS) and Clinical Global Impression - Severity (CGI-S) are assessed for schizophrenia subjects only. Montgomery-Asberg Depression Rating Scale (MADRS), Young Mania Rating Scale (YMRS) and Clinical Global Impression - Bipolar Version (CGI-BP) are assessed for bipolar I disorder subjects only. All efficacy assessments will be summarized for the efficacy sample at each mapped trial week by treatment formulation and disease type (if applicable).

PANSS total score (range 30-210) is the sum of the rating scores for 7 positive scale items, 7 negative scale items, and 16 general psychopathology scale items from the PANSS scale. A missing value for any item would result in a missing PANSS total score. PANSS positive subscale score (range 7-49) is the sum of the rating scores for the 7 positive scale items from the PANSS scale. PANSS negative subscale score (range 7-49) is the sum of the rating scores for the 7 negative scale items from the PANSS scale. CGI-S score (range 0-7), CGI-I score (range 0-7), CGI-BP severity score (range 0-7) and

Protocol 031-201-00181

CGI-BP change from preceding phase score (range 0-7) are directly retrieved from CRF data.

SWN-S total score (range 20-120) is the sum of the rating scores for 10 positive scale items (items 2+, 3+, 5+, 7+, 8+, 13+, 15+, 18+, 19+, 20+) and 10 negative scale items (items 1-, 4-, 6-, 9-, 10-, 11-, 12-, 14-, 16-, 17-). SWN-S subscale total score (range 4-24) is the sum of the rating scores for the 4 items in each of the 5 subscales: mental functioning (3+, 7+, 11-, 17-), social integration (8+, 13+, 6-, 14-), emotional regulation (18+, 20+, 4-, 10-), physical functioning (2+, 5+, 9-, 16-), and self-control (15+, 19+, 1-, 12-). For items marked with a '+', the scoring is 'not at all = 1', 'hardly at all = 2', 'a little = 3', 'somewhat = 4', 'much = 5', and 'very much = 6'. For items marked with a '-', the scoring is reversed. response choices and scoring are as follows: not at all = 6, hardly at all = 5, a little = 4, somewhat = 3, much = 2, very much = 1. A missing value of any items in the SWN-S would result in a missing total or a subscale total score.

The MADRS is utilized as the primary assessment of a subject's level of depressive symptoms and must be administered using a structured interview guide. This scale consists of 10 items each with 7 defined grades of severity on 0 to 6 scale (reported sadness, apparent sadness, inner tension, reduced sleep, reduced appetite, concentration difficulties, lassitude, inability to feel, pessimistic thoughts, and suicidal thoughts). MADRS total score is sum of 10 item score with range from 0~60. The missing score for any 1 item will result in a missing MADRS total score. MADRS total score will be summarized by trial week for each treatment formulation.

The YMRS consists of 11 items assessing the core symptoms of mania and is based on the subject's subjective report of his or her clinical condition. Additional information is based upon clinical observations made during the clinical interview. Each item has 5 defined categories of severity with 4 items graded on a 0 to 8 scale (irritability, speech, content, and disruptive-aggressive behavior) and 7 items graded on a 0 to 4 scale (elevated mood, increased motor activity/energy, sexual interest, sleep, language-thought disorder, appearance, and insight). YMRS total score is sum of 11 item score with range from 0~60. The missing score for any 1 item will result in a missing YMRS total score. YMRS total score will be summarized by trial week for each treatment formulation.

The CGI-BP scale refers to the global impression of the subject with respect to bipolar disorder. The scale rates the subject's severity of illness (CGI-BP-Severity: mania, depression, and overall bipolar illness) and change from baseline visit (CGI-BP Change from Preceding Phase: mania, depression, and overall bipolar illness) based on a 7-point scale (rang 1-7).

Protocol 031-201-00181

LOCF missing data imputation will be performed for all efficacy assessments. Changes from baseline in SWN-S total score and SWN-S subscale total score for all efficacy sample in addition to PANSS total score, PANSS positive subscale total score, PANSS negative subscale total score, CGI-Severity score, MADRS total score, YMRS total score, CGI-BP-Severity score will be summarized using descriptive statistics, if applicable. CGI-Improvement score and CGI-BP change from preceding phase score are also summarized using descriptive statistics, if applicable.

In addition, the linear mixed-effects mode will be used to explore the effect of the treatment and change from baseline over the time for efficacy endpoints, i.e. SWN-S total score, PANSS total score and YMRS total score. Change from baseline in those efficacy endpoints will be analyzed using MMRM analysis with a restricted maximum likelihood (REML) approach. Analyses will include the categorically fixed effects of treatment, disease type (if applicable), PK sample scheduling (if applicable), trial week, and treatment-by trial week interaction, as well as the covariates of baseline-score-by-week interaction in addition to subject as random effect. An unstructured covariance structure will be used to model the within-subject errors and Kenward-Rodger degree of freedom will be used to test the fixed effects. If this analysis approach fails to converge, the covariance structures of heterogeneous compound symmetry will be utilized in the analysis and the “sandwich” estimator of the variance covariance matrix of the fixed effects parameters will be used in order to deal with possible model misspecification of the covariance matrix. 95% confidence intervals (CIs) for difference of changes from baseline in efficacy endpoints or values of efficacy endpoints between aripiprazole 2M LAI 960mg and IM depot 400 mg will be provided at trail weeks as well.

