### **3.7.5.2 Clinical Global Impression - Severity**

The severity of illness for each subject will be rated using the CGI-S scale. To assess CGI-S, the rater or investigator will answer the following question: "Considering your total clinical experience with this particular population, how mentally ill is the subject at this time?" Response choices include: 0 = not assessed; 1 = normal, not ill at all; 2 = borderline mentally ill; 3 = mildly ill; 4 = moderately ill; 5 = markedly ill; 6 = severely ill; and 7 = among the most extremely ill subjects.

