### **3.7.5.3 Clinical Global Impression - Improvement Scale**

The improvement of illness for each subject will be rated using the CGI-I scale. To assess CGI-I, the rater or investigator will rate the subject's total improvement whether or not it is due entirely to drug treatment. All responses will be compared with the subject's condition at baseline. Response choices include: 0 = not assessed, 1 = very much improved, 2 = much improved, 3 = minimally improved, 4 = no change, 5 = minimally worse, 6 = much worse, and 7 = very much worse. Direct entry of the CGI-I score on the eCRF without verifiable source documentation is not acceptable.

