### 3.7.5.7 Clinical Global Impression - Bipolar Version

The CGI-BP scale refers to the global impression of the subject with respect to bipolar I disorder. The scale rates the subject's severity of illness (CGI-BP-Severity: mania, depression, and overall bipolar illness) and change from preceding phase (CGI-BP change from preceding phase: mania, depression, and overall bipolar illness) based on a 7-point scale. Severity of illness (CGI-BP-Severity) should be rated at visits as indicated in the schedule of assessments (Table 3.7-1 for sparse sampling and Table 3.7-2 for robust sampling). At each visit other than Day 1 (baseline), the change from preceding phase (CGI-BP change from preceding phase) will be judged with respect to the subject's condition at baseline for that phase (ie, the last visit from the preceding phase).

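### SAP Section 9 puts the not-assessed code 0 inside the CGI-S and CGI-I score range with no rule setting it to missing, and gives CGI-BP two different ranges

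*SAP*

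**What the plan says.** **Meaning of 0.** Protocol Section 3.7.5.2 says of CGI-S: "Response choices include: 0 = not assessed; 1 = normal, not ill at all; 2 = borderline mentally ill". Section 3.7.5.3 says of CGI-I: "Response choices include: 0 = not assessed, 1 = very much improved, 2 = much improved". Both scales end at 7, so each has seven real ratings plus one administrative code.

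**Range and source.** SAP Section 9 lists "CGI-S score (range 0-7), CGI-I score (range 0-7), CGI-BP severity score (range 0-7") and continues with "CGI-BP change from preceding phase score (range 0-7) are directly retrieved from CRF data".

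**CGI-BP.** Protocol Section 3.7.5.7 describes a 7-point scale for severity and for change, and does not mention 0. Later in SAP Section 9 the same two CGI-BP ratings are "based on a 7-point scale (rang 1-7").

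**Use.** SAP Section 9 summarises change from baseline for CGI-S and CGI-BP severity, and the score itself for CGI-I and CGI-BP change, all descriptively. LOCF applies to every efficacy scale, and the protocol (Section 7.4.2) asks for both LOCF and observed-case results.

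**Missing-value rules.** SAP Section 9 says that a missing item makes the total missing for PANSS, SWN-S, MADRS and YMRS. It has no corresponding sentence for any CGI score.

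**The concern.** A code meaning that no rating was made should not be averaged. On CGI-S and CGI-I low scores are good, so a retained 0 would count as healthier than normal or as better than the largest improvement on the scale.

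The problem could spread beyond the visit concerned. SAP Section 5.2 reports the last observation in each mapped week and uses it for carry-forward. If a 0 counts as an observation, it can displace a real rating in the same window, block imputation at that visit, and be carried into later weeks.

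A range check programmed from Section 9 would not catch this, because 0 lies inside the stated range.

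**Working it through.** **1. Reproduce the stated range.** Counting every CGI-S or CGI-I response code in Protocol 3.7.5.2 and 3.7.5.3 (0, 1, ..., 7) gives eight codes and a range of 0-7, as in the SAP. Counting real ratings only (1, ..., 7) gives 1-7. The SAP range is therefore obtained only by counting the not-assessed code as a score.

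**2. Compare with the other scales in SAP Section 9.**
- PANSS: 30 × 1 = 30 to 30 × 7 = 210; stated 30-210.
- SWN-S: 20 × 1 = 20 to 20 × 6 = 120; stated 20-120.
- MADRS: 0 to 10 × 6 = 60; stated 0-60.
- YMRS: 0 to 4 × 8 + 7 × 4 = 60; stated 0-60.

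All four ranges come from real ratings alone (0 is a real item rating on MADRS and YMRS). CGI-S and CGI-I do not follow this pattern.

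**3. CGI-BP.** A range of 0-7 has eight values. The protocol and the later SAP paragraph both say 7-point, which fits 1-7. The two SAP paragraphs cannot both be right.

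**4. Effect on a raw mean.** Let f be the share of ratings recorded as 0 and μ the true mean, with zeros unrelated to the true rating. The computed mean is (1 - f) × μ, so the shift is -f × μ. The documents give neither f nor μ, so the values below are assumptions.

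| μ | f = 1% | f = 5% |
|---|---|---|
| 3 | -0.03 | -0.15 |
| 4 | -0.04 | -0.20 |

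As counts, with 85 per group (the planned completers at the larger sample size) and μ = 3:
- one zero: -(1/85) × 3 = -0.035;
- five zeros: -(5/85) × 3 = -0.18.

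**5. Effect on change from baseline (CGI-S).** The shift in mean change is -f_post × μ_post + f_base × μ_base. For one subject truly at 3 throughout:
- a 0 after baseline gives 0 - 3 = -3 instead of 0;
- a 0 used as baseline gives 3 - 0 = +3, a false worsening.

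With equal shares and equal means at both visits the two terms cancel in the mean, although individual changes are still wrong.

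**6. Where it reaches.** The mixed model in SAP Section 9 covers SWN-S, PANSS and YMRS totals only. The sample size in SAP Section 4 rests on PK ratios only. Neither uses a CGI score.

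**The case against.** The best defence is that the SAP never says a 0 will be averaged. Taking a score directly from the CRF can simply mean that it is not a derived sum, and the printed range can be read as the range of the data field. SAP Section 5.1 limits baseline and last visit to evaluable assessments, and Section 5.3 builds the observed-case dataset from subjects evaluated at the visit. In ordinary language a rating that was not assessed is neither. This stands in part: a careful programmer could use that wording to drop the zeros, so the consequence is a risk from an omitted rule and not a stated procedure. But the general wording never names the code, and Section 9 places the code inside the score range.

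Stronger readings that a reader might infer, and why the documents do not support them:

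- **All missing CGI data are scored as very good.** Only a rating actually entered as 0 is exposed. Blank fields, missed visits and dropouts produce no 0.
- **The bias is always towards improvement.** A 0 at a CGI-S baseline acts the other way, and the two effects can offset each other in a mean change.
- **The same fault applies to CGI-BP.** No document defines 0 for that scale. The demonstrated fault is the contradictory range.
- **The bias favours one arm.** Under the COVID-19 measures in SAP Section 7.5, sparse-schedule subjects have only remote safety assessments between dosing visits. Days 29 and 197 are efficacy visits that are dosing days for 400 mg but not for 960 mg, so unrated visits could be more common with 960 mg. The documents do not say that such visits would be entered as 0 rather than left blank, and otherwise CGI is scheduled on the same days in both arms. A differential bias is not shown.

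**Conclusion.** The point holds as a wrong stated range with a missing rule. For CGI-S and CGI-I the valid range is 1-7, and the SAP should say what happens to 0. For CGI-BP the two ranges in Section 9 must be reconciled.

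The size cannot be determined from the documents, because the CRF is not among them and no frequency of zeros is given. The illustrative shift of -0.03 to -0.20 points in a raw mean rests on an assumed true mean of 3 to 4, an assumed 1% to 5% of zeros, zeros unrelated to the true rating, and no carry-forward. It is not a forecast.

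This is a minor point. It touches secondary, descriptive efficacy summaries and leaves the trial's main conclusions alone.

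**What to change.** In SAP Section 9, give the range as 1-7 for CGI-S, CGI-I, CGI-BP severity and CGI-BP change, in both places where CGI-BP appears. Add one sentence: a CGI-S or CGI-I code of 0, and any 0 recorded for CGI-BP, is set to missing before the baseline, observed-case, LOCF and change-from-baseline derivations.

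The cost is one sentence and the corrected ranges in the SAP, plus one recoding step in the programming. Data collection, trial conduct and sample size do not change.
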